in-person. Participants will be asked to sign the electronic consent form on Qualtrics or REDCap, mail a signed paper version back to the research assistant, or drop off a signed paper version to their clinic for research staff to pick up. Alternatively, consenting maybe be done in-person. Participants will also keep a copy of the consent for their records.

Participants randomized to the MORE condition will participate in eight, weekly, two-hour online group sessions led by a clinic or study counselor. Each session will contain 5 to 9 participants and will be conducted online through secure video or phone conferencing. If a participant is unable to join the MORE session through video conference due to technical difficulties at the time of the session, the participant will be instructed to join the session by phone or the participant may go to their clinic and a research or clinic staff member can help them access the intervention through their tablet or a computer. Attendance at each session and reasons for missing sessions will be recorded. Participants randomized to the control condition will continue receiving treatment as usual at their clinic.

All study participants will partake in a total of three interviews lasting up to 120 minutes occurring at baseline, 8-, and 16-weeks (week 1 will be considered the week of the first MORE group session) by video or phone conferencing or in-person. If more than 3 months since baseline survey was administered from start of group (study intervention), clients will be asked to do another baseline survey. Each participant will also have a urine or saliva sample collected during each assessment. This is required to verify self-report of drug use. Due to social desirability, it is common for people to not accurately report drug use; therefore, biochemical verification is the gold standard measure of drug use. Participants will be mailed a urine or saliva test prior to the interview.

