1.9 Interviews, Focus Groups, or Surveys

A. Administration

Timing and Frequency

Research staff will collect interview data and drug screens from both intervention and control group subjects through video, phone interview, or in-person using standardized measures conducted at baseline and 8- and 16-weeks. Cognitive testing data will be collected at baseline and 8-weeks. If the research assessments are conducted over the phone, drug screen results will be recorded as self-reported. Additionally, subjects will engage in twice-daily EMA assessments of approximately 3-5 minutes each for 16-weeks. For 16-weeks, subjects will also initiate EMA communications to report lapses or serious cravings, which will also last for under 5 minutes. For those who do not complete their EMA, our research staff will do a timeline follow-back over the phone or video conferencing to collect missing EMA drug use data. EMA completion reports will be reviewed, weekly, and participants will be contacted, as needed, to collect missing daily drug use data.

Location

The assessments and drug screens will take place via video/online, phone interview, at their clinic, or at another safe and private location in the community (e.g., library, park, or coffee shop).

Procedures for Audio and Visual Recording

Audio or video recordings will be made of the MORE therapy sessions. All recordings will be stored in password protected computers, in a locked office at [name], or in password protected files, on the Rutgers network or HIPAA compliant Box file.

9

B. Study Instruments

Version Number: 15, 2/2/2022 Protocol Number: Pro20190016877 PI Name: [name]

Protocol Title: Mindfulness Oriented Recovery Enhancement (MORE) as an Adjunct to Methadone Treatment RESERVED FOR IRB STAMP
DO NOT MODIFY THIS SPACE

- Time until first opioid lapse assessed through ecological momentary assessment data and timeline follow-back.
- Time until MMT dropout assessed through clinic records (abstracted by the study counselor who will have access to the clinic records). Time until dropout will be calculated from enrollment until last dose of methadone.
- Total days of methadone treatment assessed through clinic records (abstracted by the study counselor who will
 have access to the clinic records). Number of days will be calculated from enrollment until each follow-up timepoint.
- Total days of opioid or any drug use assessed through EMA data and timeline follow-back

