Data will be received by the REDCAP or Qualtrics system. Data access between the REDCap and Qualtrics databases and the web servers aew encrypted and restricted to a monitored port. All REDCap and Qualtrics data, which is displayed or captured by the user interface, is encrypted for security. Within REDCap and Qualtrics all data transactions including inserts, updates, deletions, import/export and reporting are logged. The EMA system in this study deployed via REDCap and Qualtrics will reside in a HIPAA compliant protected space. The REDCap and Qualtrics production and development servers use encrypted drives. Physical hardware will be secured in a locked facility.

The data will only be accessible to study investigators and staff. The data will be processed by an already developed REDCap or Qualtrics program that formats the data as a "long file" with one row per time point per individual participant. The investigators will employ linear mixed models to test the effects of MORE vs. the control condition on substance use, craving, pain, and other study variables. The treatment X time interaction will be the main fixed effect of interest. Models will include a random intercept, as well as a random slope if warranted by model fit statistics. Auto-correlation between repeated measures will be modeled as a first-order autoregressive function. We will also compute within-group linear mixed models examining mindfulness practice duration as a predictor of clinical outcomes.

EMA completion reports will be reviewed, weekly, and, as needed (at a maximum weekly), we will conduct a timeline follow-back⁹ with each participant to account for missing EMA drug use data. The timeline follow-back is a

10

Version Number: 15, 2/2/2022 Protocol Number: Pro20190016877 PI Name: [name]

Protocol Title: Mindfulness Oriented Recovery Enhancement (MORE) as an Adjunct to Methadone Treatment RESERVED FOR IRB STAMP DO NOT MODIFY THIS SPACE

reliable and valid measure where participants are asked to recall and record events (e.g., drug use) within a specified time period on a calendar.

Substance use history (Baseline). We will use the PhenX Toolkit-Substance Abuse and Addictions Core Tier 1 Collection⁸ to gather self-report information on lifetime use of opiates, alcohol, tobacco and substances, and past-30 day use of all substances.

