Hypothesis 1.1. (**Primary Outcome**) MORE will result in longer duration of time to first opioid lapse and MMT dropout than TAU. We will use survival analysis (Kaplan Meier curves and marginal model analysis for multivariate survival data)³⁴ to test effects of MORE vs. TAU on time until first opioid lapse and MMT dropout—evidenced either on EMA, Timeline Follow-Back, urinalysis or medical records (whichever is first). Survival analysis will be run once, at 16 weeks post-baseline. Clustering within cohort will be adjusted in the multivariate marginal model analysis.³⁴ We will estimate the hazard ratios of opioid lapse and MMT dropout when comparing MORE with TAU, controlling for covariates.

Hypotheses 1.2 and 1.3 (Secondary Outcomes). MORE will result in more days of opioid abstinence (or less days of use) and a higher rate of biochemically-verified abstinence over time than TAU. Generalized linear mixed model (GLMM)³⁵ repeated measures analysis will be used. Specifically, identity link will be used for "number of abstinent days" as the dependent variable, and logit link will be used for "opioid abstinence (yes/no via urinalysis)" as the dependent variable. Days of use/abstinence will be assessed via EMA, number of drug use days since last visit and past 30 days, and the Timeline Follow-Back. In cases of conflicting findings across data sources, we will assume the highest number of days of use or lowest number of abstinent days recorded for that period. Analyses will include group (MORE vs. TAU), time, and group by time interactions as the fixed effects independent variables. Correlations among repeated measures and among subjects within cohorts will be modeled using nested random effects. Potential confounders that meet the p<0.10 criterion stated above will be entered as covariates. Linear contrasts will be constructed to test between-group differences in "days of use" or "days of abstinence" separately at each timepoint. In comparing days of use, if a substantial proportion of subjects do not use opioids, resulting in excessive zero days of use, we will use a two-part logistic/linear analysis model.^{36,37}

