Hypotheses 1.4 (**Secondary Outcomes**). MORE will result in more days of MMT and greater decreases in pain severity, pain interference, days of non-opioid drug use, and emotional distress over time than TAU. We will use GLMM to compare days of MMT, pain severity and interference scores, days of non-opioid drug use, and emotional distress among the treatment groups, using the same analytic strategy described above.³⁵

AIM 2 Analyses. Mediational analysis. To test whether the three mediators specified in Aim 2 statistically mediate the effect of treatment on changes in days of opioid use over time, we will conduct a multivariate path analysis via a latent growth curve framework conducted in structural equation modeling software (i.e., MPlus) according to established guidelines³⁸ evaluating 3 regression paths for each mediator: A) 'a' path between treatment indicator and pre-post treatment change in the mediator (e.g., savoring); B) the 'b' path between pre-post treatment change in the mediator (e.g., savoring) and the latent slope (change) of the outcome (e.g., opioid use); and C) the 'c' path between treatment indicator and the latent slope of the outcome (e.g., opioid use). We will emulate similar multivariate analyses from published studies of meditation interventions^{39,40} by testing treatment effects on the latent slope of changes in days of drug use over time as mediated by changes in proposed mechanisms. We will test mediation by evaluating the significance of the joint product of the a and b paths, with bootstrapping used to test the significance of the indirect effect. A similar model will be estimated for changes in pain severity. Path models will be corrected for multiple comparisons. Simultaneous estimation of mediational effects from all three mediators to days of drug use and pain will allow us to determine unique effects of the core therapeutic mechanisms of MORE (mindfulness, reappraisal, savoring) – representing one of the most comprehensive mediation modeling attempts of the MORE intervention research program to date.

Version Number: 15, 2/2/2022 Protocol Number: Pro20190016877 PI Name: [name]

Protocol Title: Mindfulness Oriented Recovery Enhancement (MORE) as an Adjunct to Methadone Treatment RESERVED FOR IRB STAMP
DO NOT MODIFY THIS SPACE

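### Cumulative days of methadone treatment need a visit-specific variance: with random intercepts and one residual variance, the natural but unstated reading, the week-16 contrast rejects too often

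*Combined protocol and SAP*

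**What the plan says.** Section 1.9 B takes total days of methadone treatment from clinic records and defines the count cumulatively: "Number of days will be calculated from enrollment until each follow-up timepoint". Assessments are set as "occurring at baseline, 8-, and 16-weeks" (section 1.3 A).

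More days of MMT is part of Hypothesis 1.4 in section 6.1 A: "We will use GLMM to compare days of MMT, pain severity and interference scores". That paragraph adopts the strategy given for Hypotheses 1.2 and 1.3, which has these parts:

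- Link, for number of abstinent days: "Specifically, identity link will be used for" that outcome. MMT days, also a day count, inherits it.
- Fixed effects for group, time and their interaction.
- Covariance: "Correlations among repeated measures and among subjects within cohorts will be modeled using nested random effects".
- Tests: "Linear contrasts will be constructed to test between-group differences in" days of use or abstinence, separately at each timepoint.

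No section states a visit-specific variance, an unstructured covariance or robust standard errors for this outcome. The sensitivity analyses in section 6.1 A cover site, cohort, therapist and missing data, but not unequal variance across visits. The only other mixed-model text is in the ecological momentary assessment (EMA) part of section 1.9 B: "Models will include a random intercept, as well as a random slope if warranted by model fit statistics", and "Auto-correlation between repeated measures will be modeled as a first-order autoregressive function".

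**The concern.** The week-16 count contains the week-8 count, and at enrollment the count is zero for everyone. Its spread must therefore widen over time, because differences between participants accumulate. A model with participant and cohort intercepts and one residual variance assumes the same total variance at every visit. It estimates the average across visits, which is too small for week 16 and too large for week 8. A baseline row of zeros pulls the average down further.

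At stake is the error rate of a named secondary comparison. With no effect of MORE, the week-16 contrast would be declared significant too often. A real difference at week 8 would be hard to detect.

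**Working it through.** The plan gives no variance, power or error rate for MMT days, so there is no figure of its own to reproduce.

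**Inputs from the documents.** Visits at 56 and 112 days (8 and 16 weeks); up to 92 per group (section 1.5); about 50% of people starting MMT discontinue within 12 months (section 1.2).

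**Assumptions.** Exponential dropout, complete data, no treatment effect, no cohort effect, and one unadjusted two-sided 5% contrast.

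**Formula.** With balanced data and saturated group-by-time means, the intercept model gives each visit the mean variance V̄ over the k visits entered. The actual error rate at visit t is

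α(t) = 2[1 − Φ(1.96 √(V̄ / V(t)))].

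**Variances.** With λ = ln 2 / 365 per day, days in treatment up to t have variance

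2[1 − e^(−λt)(1 + λt)]/λ² − [(1 − e^(−λt))/λ]².

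This is 100.0 at day 56 (SD 10.0) and 720.6 at day 112 (SD 26.8), a ratio of 7.2.

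**Weeks 8 and 16 only.** V̄ = (100.0 + 720.6)/2 = 410.3.
- Week 16: √(410.3/720.6) = 0.755; 1.96 × 0.755 = 1.48; α = 13.9%.
- Week 8: √(410.3/100.0) = 2.03; 1.96 × 2.03 = 3.97; α below 0.1%.

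**Baseline zeros entered.** V̄ = (0 + 100.0 + 720.6)/3 = 273.5.
- Week 16: √(273.5/720.6) = 0.616; 1.96 × 0.616 = 1.21; α = 22.7%.
- Week 8: √(273.5/100.0) = 1.65; 1.96 × 1.65 = 3.24; α = 0.1%.

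A simulation of 20,000 null trials with 92 per arm gave 13.9% and 22.9% at week 16, and below 0.1% at week 8 in both cases.

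**Other assumed distributions** (same formula):

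| Scenario | Variance ratio | Week 16, two visits | Week 16, with zeros | Week 8, two visits | Week 8, with zeros |
|---|---|---|---|---|---|
| Dropout median 180 days | 6.5 | 13.7% | 22.4% | <0.1% | 0.2% |
| Dropout median 365 days | 7.2 | 13.9% | 22.7% | <0.1% | 0.1% |
| Dropout median 1000 days | 7.7 | 14.1% | 22.9% | <0.1% | 0.1% |
| Person-level adherence, no dropout | 3.7 | 11.8% | 20.2% | 0.3% | 1.4% |
| Independent daily attendance | 2.0 | 9.0% | 16.6% | 1.6% | 5.0% |
| Median 365 days, 0-90 day wait from enrollment to week 1 | 2.1 | 9.3% | 17.0% | 1.4% | 4.6% |

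Simulation gave slightly more for the 1000-day median (14.7% and 23.8%). A 0-120 day wait gives 8.5% and 15.9% at week 16, and 2.0% and 5.7% at week 8. As the variance ratio grows without limit, the two-visit rate approaches 2[1 − Φ(1.96 √(1/2))] = 16.6%. The two-visit range is therefore 9-15% in the scenarios, with a ceiling of 17%.

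**Other covariance choices** (365-day median):
- AR(1) residuals with constant variance: week 16 at 13.9% (two visits) or 20.8% (with zeros).
- Intercept plus slope: 5.0% at both visits with two visits; 1.4% at week 8 and 6.3% at week 16 with zeros.
- A separate variance per visit: 4.7-5.1% at both visits in simulation.

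**Group-by-time test.** Let C be the covariance of the two counts. With two visits the model's variance for change is 2 × [(V8 + V16)/2 − C] = V8 + V16 − 2C, which is the true variance of the change. Simulated size was 5.0-5.3% across scenarios. With zeros, the residual variance becomes (V8 + V16 − C)/3, and the two-degree-of-freedom test rejected in 7.7-8.1% of null trials (5.9% under independent attendance).

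**The case against.** A reader might infer that the plan as written has a week-16 false-positive rate of 14-24% and a week-8 rate near zero. The documents do not support that unconditional reading.

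- **The model is inferred.** Section 6.1 A says nested random effects, not intercepts only. The EMA text allows a random slope, which a count with growing variance would favour and which removes most of the inflation. This stands as a condition on the result. It is not a safe rescue: Hypothesis 1.4 points to the strategy in section 6.1 A, the slope is optional, and with two visits an intercept, a slope, their covariance and a residual make four parameters for three covariance elements. With baseline zeros and a 0-90 day wait, the slope model gives 10.1% at week 8 and 3.9% at week 16.
- **The baseline row is assumed.** Section 1.9 B counts days only to each follow-up. The upper range applies only if zeros are entered.
- **The count is not capped at 56 and 112 days.** It starts at enrollment, while week 1 is the first MORE session (section 1.3 A). Cohorts wait for 10-18 recruits (section 4.3), and section 1.3 A provides for gaps above three months. A variable wait lowers the variance ratio, hence the wide ranges.
- **The dropout figure is borrowed.** It concerns people starting MMT; this trial enrols people already on methadone (section 4.2 D). Varying the dropout rate changes the result little.
- **The two-visit group-by-time test is sound.** This stands in full.
- **Bonferroni-Holm applies** (section 6.1 A), with the family size not given. It changes the threshold but does not repair the standard error. At a 1% threshold the two-visit rate would be 2[1 − Φ(2.576 × 0.755)] = 5.2%.
- **Total days through week 16 is a legitimate quantity.** That it includes weeks 1-8 is no fault, provided nobody reads it as an effect in weeks 9-16.

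**Conclusion.** The concern holds conditionally. The outcome is cumulative, its variance grows, and the stated strategy makes no provision for that while testing each timepoint. Under participant and cohort intercepts with one residual variance, the unadjusted week-16 contrast is too liberal in every scenario tried, and the week-8 contrast is conservative or close to nominal. The size depends on three things the plan leaves open: the covariance structure, whether a baseline row enters, and how long participants wait between enrollment and week 1. It also depends on the assumed distribution of days.

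Severity is moderate. One secondary outcome is affected, and Hypothesis 1.1 tests retention separately as time to MMT dropout, which this problem does not touch.

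**What to change.** For MMT days, replace the inherited strategy with a short specification:

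1. Define the start date of the count. It should be the same point in the trial for both arms, so that waiting time does not enter the outcome.
2. Enter no baseline row.
3. Choose one analysis in advance. Either keep the mixed model for weeks 8 and 16 with an unstructured or visit-specific covariance, or with robust standard errors; or analyse total days once, at week 16, over a fixed 112-day window with cohort-robust standard errors.
4. If separate period effects are wanted, use days 1-56 and 57-112 as non-overlapping outcomes, each with its own variance.

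Cohorts of 10-18 and up to 184 participants imply about 184/18 ≈ 10 to 184/10 ≈ 18 cohorts. Any cohort-robust standard error should therefore carry a small-sample correction.

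No new data are needed. The first option in step 3 costs a few more covariance parameters: an unstructured two-visit covariance has three, against two for an intercept and a residual. It keeps the group-by-time test. The single week-16 analysis gives that test up for this outcome.

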Current substance use (Baseline, 8- and 16-- weeks). We will utilize a urine or saliva screen that tests for buprenorphine and methadone (to provide corroboration of MAT engagement and compliance) and additional substances (e.g., benzodiazepines, barbiturates, cocaine, marijuana, methamphetamine, morphine, oxycodone, phencyclidine and amphetamine). Participants will also be asked about overall number of days of use in the past 30 with questions based on PhenX Toolkit-Substance Abuse and Addictions Core Tier 1 Collection. For those prescribed opioids for pain, misuse will be assessed with the Current Opioid Misuse Measure. Drug test results conducted by the clinic during the study period will be obtained from participants' clinic charts. We will combine self-reports of opioid relapse and other drug use with biochemical measures because it is the gold standard, and without biochemical verification, self-reported drug use as an outcome variable will be questioned by the scientific community. If a biochemical measure is negative, but the participant reports drug use, the participant will be coded as using drugs since the biochemical measure will only capture a specific time point. However, if the participant self-reports drug abstinence, but the biochemical measure is positive for drug use (the more likely scenario) the participant will be coded as having used drugs.

Craving (Baseline, 8- and 16-- weeks). Opioid and other drug craving will be assessed with an adapted version of the Penn Alcohol Craving Scale (PACS)¹⁰ and the Craving Suppression Scale. The PACS is a valid, reliable, and internally consistent measure that consists of five self-report items that have been found to predict relapse. The items assess the intensity, frequency, ability to resist, and duration of craving. Originally developed to assess alcohol craving, it has been adapted and used to measure craving for various substances, including opioids,¹¹ and adapted versions have been used in trials of mindfulness-based interventions for substance use.¹² The Craving Suppression Scale is a 17 –item measure that assesses how individuals cope with craving

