Cognitive impairment, psychosis, suicidality (screening). If cognitive functioning, current psychosis, and suicidality is questionable based on information provided by clinic staff, patient history, or research staff observation, to determine study eligibility, cognitive impairment will be assessed with the Mini Mental Status Exam (MMSE),²⁰ psychosis will be assessed with the Structured Clinical Interview for DSM-V (SCID) Psychotic screen,²¹ and suicidality will be assessed with the Columbia Suicide Severity Rating Scale (C-SSRS). The Mini-Mental Status Exam, MMSE is a widely used valid and reliable measure of cognitive functioning that assesses orientation to time and place, registration, attention and calculation, recall, language, Scores <24 indicate cognitive impairment. The SCID Psychotic Screen is a semi-structured clinical interview that assesses symptoms of psychotic disorders (e.g., delusions, hallucinations) based on the DSM-V criteria. The C-SSRS is a five-item reliably and valid measure that assesses suicidal ideation, plans, and intent.

Mental health history (Baseline), trauma (baseline, 8-weeks, and 16-weeks) and psychiatric symptoms and treatment (baseline, 8 weeks, 16 weeks). At baseline, history of mental illness and psychiatric treatment will be assessed. At each subsequent research visit, participants will be asked if they took any psychotropic medications or received any mental health counseling since their last visit. Trauma history will be assessed with the Brief Trauma Questionnaire (BTQ). ^{23,24} The BTQ is a 10-item self-report questionnaire that assesses traumatic experiences. At each research visit, symptoms of depression and anxiety will be evaluated with the Center for Epidemiologic Depress Scale and the Beck Anxiety Inventory. ²⁵

Physical health history (Baseline) and symptoms (Baseline, 8- and 16-- weeks) and medication (Baseline, 8- and 16-- weeks). At Baseline, history of illness such as HIV, cancer, heart disease, emphysema, asthma and other chronic conditions will be assessed. Daily health functioning will be evaluated at every research visit with the RAND 36-ltem Health Survey 1.0 (SF-36).²⁶ The reliability and validity of this self-report scale that measures overall health and ability to complete daily activities has been shown. Current pain and other medication (prescribed and over the counter) will be assessed at each research visit.

12

Version Number: 15, 2/2/2022 Protocol Number: Pro20190016877

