C11. Outcomes and Future Directions. We expect to establish the efficacy of an innovative intervention that can enhance MAT by supporting chronic pain management and MMT adherence while preventing drug use and opioid relapse. Results from this study will inform the development of services in New Jersey and other states seeking efficacious strategies to combat the opioid epidemic. If this study demonstrates MORE's efficacy as an adjunct to MMT, we will follow this study with a Stage IV implementation/dissemination study to enhance the rapidity and fidelity of uptake of the intervention into standard of care for persons with OUD.

B. Provide a power analysis. (As applicable, e.g. quantitative research)

We powered the R33 study based on data from prior research. We used a study of an MBI for substance users,⁴ which showed that the hazard ratio of relapse to drug use for the intervention compared to TAU was 0.46. We thus assumed a similar, but more conservative hazard ratio of relapse to opioid use of MORE compared to TAU at about 0.55. (We are using a slightly more conservative hazard ratio than in the original application due to the increased power obtained by reducing the number of treatment conditions from three to two.) We also assumed that the median relapse time to opioid use is 99 days, based on a prior study of relapse to drug use in a general MMT population.⁵ With 1.5 years of subject accrual and an additional follow-up of 16 weeks after the accrual interval, our study needs 47 subjects per group to test a hazard ratio of 0.55 when comparing MORE to TAU, with 80% power and alpha=5% (two-sided). To account for attrition, we will recruit 85 subjects per group (a total of 184 subjects at a 1:1 ratio for MORE vs. TAU).

Version Number: 15, 2/2/2022 Protocol Number: Pro20190016877

PI Name: [name]
Protocol Title: Mindfulness Oriented
Recovery Enhancement (MORE) as an
Adjunct to Methadone Treatment

RESERVED FOR IRB STAMP DO NOT MODIFY THIS SPACE

C. Describe the steps that will be taken secure the data (e.g., training, authorization of access, password protection, encryption, physical controls, certificates of confidentiality, and separation of identifiers and data) during storage, use, and transmission.

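### The rule that a positive screen overrides reported abstinence makes no provision for a documented opioid prescription, so compliant prescribed use can count as failed abstinence and possibly as a first lapse

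*Combined protocol and SAP*

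**What the plan says.** Section 1.9 B (Current substance use) describes a urine or saliva panel whose listed substances include morphine and oxycodone. Methadone and buprenorphine are on it to corroborate treatment. The participant is coded as having used drugs "if the participant self-reports drug abstinence, but the biochemical measure is positive for drug use". Drug tests run by the clinics during the study are also taken from the charts.

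The same paragraph recognises prescribed use: "For those prescribed opioids for pain, misuse will be assessed with the Current Opioid Misuse Measure". Later in 1.9 B, under physical health, the plan adds: "Current pain and other medication (prescribed and over the counter) will be assessed at each research visit". The eligibility criteria in 4.2 D require chronic non-malignant pain and do not exclude people prescribed opioids.

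Two outcomes can be touched:

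- **Primary, time to first opioid lapse.** Section 6.1 A, Hypothesis 1.1, takes the event as "evidenced either on EMA, Timeline Follow-Back, urinalysis or medical records (whichever is first". The instrument list in 1.9 B names only EMA and timeline follow-back.
- **Secondary, opioid abstinence.** Section 6.1 A, Hypotheses 1.2 and 1.3, analyses a yes/no abstinence outcome determined by urinalysis.

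Neither section says how the misuse measure or the medication record changes the coding of a positive screen.

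**The concern.** When collecting data, the protocol separates prescribed use from misuse. When coding outcomes, it drops the distinction. A participant who takes a prescribed opioid as directed, reports no illicit use and screens positive for oxycodone meets the written condition for the override. Following the rule as written records a failure that is not a relapse. The alternative is for staff to make exceptions case by case, and the protocol describes no blinded adjudication for that.

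False events that occur at the same rate in both arms dilute the treatment effect and use up power. False events whose rate depends on arm bias it in a direction that cannot be known in advance. The second case is plausible here because MORE is aimed at pain.

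**Working it through.** **Inputs from section 6.1 B.** Design: "hazard ratio of relapse to opioid use of MORE compared to TAU at about 0.55"; "We also assumed that the median relapse time to opioid use is 99 days" (arm not named); "With 1.5 years of subject accrual and an additional follow-up of 16 weeks after the accrual interval"; "with 80% power and alpha=5% (two-sided"). Section 1.3 C gives each participant 16 weeks (112 days). The total of 184 at 1:1 is 92 per arm, although 6.1 B also says 85 per group. The share prescribed a detectable opioid is not given and is called f below.

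**The plan's own figure, 47 per group.** Schoenfeld events = (1.960 + 0.842)² / (0.25 × (ln 0.55)²) = 87.8. With exponential survival, λ = ln 2 / 99 per day in TAU, uniform accrual A = 1.5 × 365.25 = 547.9 days and minimum follow-up F = 112 days, the event probability is 1 − (e^(−λF) − e^(−λ(A+F))) / (λA). This gives 0.884 in TAU and 0.729 in MORE, mean 0.806, hence 87.8 / 0.806 / 2 = 54.5, or 55 per group. If the 99-day median belongs to MORE, the result is 47.5, or 48. Freedman's 94 events divided by 2 is exactly 47. The stated figure is therefore reached only under particular readings. None of this affects the coding question.

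**Reference case, no miscoding.** With 112 days each and the 99-day median in TAU, event probabilities are 1 − e^(−112λ) = 0.543 and 1 − e^(−0.55 × 112λ) = 0.350, mean 0.447. At 184 participants that is 82.2 events. Power = Φ(√(82.2/4) × |ln 0.55| − 1.960) = Φ(0.75) = 77%, before attrition and clustering.

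**With miscoding.** A share f of both arms receives a false event at the first positive screen, unless a true lapse comes earlier. The Cox hazard ratio comes from simulation with 400,000 participants (error about 0.005; the f = 0 runs gave 0.546 to 0.553). The first positive is placed at day 14 or 28 (a clinic test), day 56 (week-8 screen) or day 112 (week-16 screen). Power is the Schoenfeld value at 92 per arm for the diluted hazard ratio.

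| Assumed f | HR, day 14 | Day 28 | Day 56 | Day 112 | Power range |
|---|---|---|---|---|---|
| 5% | 0.585 | 0.583 | 0.579 | 0.570 | 71–75% |
| 10% | 0.616 | 0.611 | 0.600 | 0.585 | 65–73% |
| 20% | 0.674 | 0.661 | 0.645 | 0.622 | 51–68% |
| 30% | 0.726 | 0.711 | 0.687 | 0.649 | 40–63% |

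Check on the event count: with f = 10%, the expected event fraction is 0.9 × 0.447 + 0.1 = 0.502; the day-56 run gave 0.502.

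**Urinalysis abstinence.** Suppose prescribing is unrelated to true abstinence and is always detected. Observed abstinence is then (1 − f) × p, and a true risk difference shrinks by the factor 1 − f: 0.95, 0.90 or 0.80 at 5, 10 or 20%. If the shares differ by arm and MORE has no effect on abstinence, the observed difference is p × (f_TAU − f_MORE). With 10% against 5%, that is a spurious 0.05p in favour of MORE.

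**The case against.** The strongest reply is that the override resolves a conflict between self-report and test. Section 1.3 A explains that testing is there because people under-report. A participant who discloses a prescription is arguably not in conflict with the test, and the sentence on the misuse measure can be read as handling prescribed users by misuse rather than by detection. Counting every detected opioid is also a defensible conservative choice. This shows that the text is open to more than one reading. It does not supply a rule, because nothing connects the misuse measure or the medication record to the coded outcome.

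Several stronger readings are tempting and are not supported:

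- **That any positive screen becomes a lapse.** Methadone and buprenorphine are tested to confirm treatment, and a cocaine or benzodiazepine positive is not an opioid lapse. The rule's term is drug use, not lapse.
- **That prescribed opioids are ignored.** They are measured in two ways; the gap is in the coding.
- **That prescribed participants certainly enter the primary analysis as lapses.** This holds only if 6.1 A governs. Under the instrument list in 1.9 B, a screen does not define the primary event.
- **That the hazard ratio is diluted.** This needs a non-trivial share, balanced between arms. Section 1.2 says practitioners are reluctant to prescribe opioids to people with this history, which points to a low share.

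It is also fair to object that the simulation assumes complete detection and full follow-up. Section 1.3 A expects some tests to be missed, and the 92 per arm is meant to absorb attrition.

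**Conclusion.** The gap is real and should be closed before outcomes are coded. Taken literally, the rule in 1.9 B fails compliant prescribed users on urinalysis-verified abstinence, whichever list of primary event sources applies. It gives them a primary event only if 6.1 A prevails over 1.9 B.

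The size is conditional. At 5% prescribed the effect is small: a hazard ratio of about 0.57–0.59 instead of 0.55, and 2 to 6 points of power lost from 77%. At 20% it is material, with a hazard ratio of 0.62–0.67 and power of 51–68%. These figures rest on assumed shares, equal prescribing in both arms, certain detection, a 99-day TAU median, and no attrition or clustering. The direction is toward 1 only under balance. If MORE lowers prescribed opioid use, the same rule would exaggerate its benefit; if MORE raises it, the rule would understate it.

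**What to change.** Add one rule to the outcome coding in 1.9 B and refer to it in 6.1 A:

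1. A morphine or oxycodone positive consistent with a prescription documented for that period is not by itself a lapse or failed abstinence. The source is the visit medication record or, for clinic tests between visits, the clinic chart where available.
2. The exemption falls away if self-report, another non-prescribed opioid, or the Current Opioid Misuse Measure indicates misuse. The cut-off for that measure must be fixed in advance, because the documents give none.
3. State how a positive is coded when neither record covers the period.
4. Code blind to arm, and report the any-positive coding as a sensitivity analysis.
5. Reconcile 1.9 B with 6.1 A on which sources define the primary event.

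The cost is small but not nil. The visit medication record and misuse measure are already planned. Chart abstraction in 1.9 B is described for methadone dose, treatment days and services, so prescriptions between visits may need an added field. Some misuse of prescribed opioids may be missed, and prescriptions rest partly on self-report, which gives back a little of what biochemical verification was meant to secure. The sensitivity analysis shows how much that matters.
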